2.1 PROTOCOL SYNOPSIS

The protocol synopsis is provided in [Appendix 1](#) and the schedule of assessments is provided in [Appendix 2](#). The study flow chart is provided in [Figure 1](#) in Appendix 2.

2.2 ENDPOINTS

This study will evaluate the efficacy and safety of tenecteplase compared with placebo. Specific objectives and corresponding endpoints for the study are outlined below.

2.2.1 Primary Efficacy Endpoints

The primary endpoint is the ordinal mRS score at Day 90.

2.2.2 Secondary Efficacy Endpoints

The following secondary efficacy endpoints are defined:

- Proportion of patients with functional independence, defined as an mRS of 0–2 at Day 90 from randomization.
- Proportion of patients with angiographic reperfusion (Thrombolysis in Cerebral Infarction [TICI] 2b or TICI 3) at completion of angiographic procedure (endovascular patients only).
- Median National Institutes of Health Stroke Scale (NIHSS) score at Day 90 from randomization.
- Proportion of patients with a Barthel Index (BI) score ≥ 95 at Day 90 from randomization.
- Proportion of patients with a good recovery based on the Glasgow Outcome Scale (GOS) at Day 90 from randomization.
- Proportion of patients with reperfusion at 24 hours post-randomization, defined as $>90\%$ reduction in $T_{max}>6s$ lesion volume.
- Proportion of patients with recanalization at 24 hours post-randomization, defined as complete recanalization on computed tomography angiography (CTA)/magnetic resonance angiography (MRA).

Further detail is described in Section [4.6.2](#).

2.2.3 Exploratory Efficacy Endpoints

The following exploratory efficacy endpoints will be analyzed:

- Median final infarct volumes at 72-96 hours visit or discharge (if patient is being discharged prior to 72-96 hours visit).
- Median infarct growth at 72-96 hours visit or discharge (if patient is being discharged prior to 72-96 hours visit).
- Ordinal mRS score at Day 90 by occlusion type (M1/ICA or M2 occlusions).
- Ordinal mRS score at Day 30 and Day 90 by randomization site (ECC or nECC).
- Proportion of patients who are randomized at an nECC and transferred to an ECC for endovascular therapy for whom planned thrombectomy was not performed.
- Proportion of patients readmitted within 30 days from discharge.
- Proportion of patients requiring one pass with endovascular therapy device (endovascular patients only).
- Mean Quality of Life in Neurological Disorders (Neuro-QoL) scores by domain.
- Proportion of patients where planned thrombectomy was not performed.
- Overall survival at Day 90.

2.2.4 Pharmacokinetic Endpoints

No pharmacokinetic endpoints are planned for this study.

2.2.5 Safety Endpoints

The safety endpoints include:

- Incidence of symptomatic intracranial hemorrhage (sICH) within 36 hours.
- Incidence and severity of adverse events (AE).
- Mortality rate up to Day 30 and Day 90.
- Proportion of patients with parenchymal hematoma type 2 (PH2) at the 72-96 hours visit.

Further detail is described in Section 4.8.

2.3 DETERMINATION OF SAMPLE SIZE

Approximately 456 patients will be enrolled in this study. Assuming the distribution of mRS scores at Day 90 in the two treatment arms as shown in [Table 1](#) and a 5% dropout rate in the study, approximately 228 patients in each treatment group will provide at least 90% power to detect the specified difference in the distribution of the mRS scores at the 2-sided 0.049 significance level (after adjustment for one efficacy interim analysis). This corresponds to being able to detect a common odds ratio (OR) of at least 1.76 (tenecteplase vs. placebo), with a total sample size of approximately 432 evaluable patients, assuming a 5% dropout rate.

Table 1 Assumed Distribution of 90-Day mRS in Use in Sample Size Determination

mRS	0	1	2	3	4	5	6
Tenecteplase (% of patients)	17	20	16	15	13	7	12
Placebo (% of patients)	13	13	12	14	18	12	18

mRS = modified Rankin Scale

The sample size estimation is highly dependent on the distribution assumption of 90-day ordinal mRS score for both treatment arms; thus, additional power calculation were performed with 456 total patients, assuming 5% drop-out rate, for different distribution scenarios on the mRS at Day 90, derived from previous stroke studies. These resulted in >88% and >99% power to detect the specified difference in the distribution of the mRS scores. For more details, see Section 6.1 of the Protocol.

2.4 ANALYSIS TIMING

This study has two planned safety interim analyses and one planned efficacy interim analysis. The safety interim analyses will occur when the first 25 and 50 patients have completed the 72-96 hours assessment post-randomization, respectively. More information on the safety interim analyses is available in Section 3.3.

The efficacy interim analysis will occur when 50% (i.e., 228) of the total patients have completed the 90-day assessment to monitor both the efficacy and safety of tenecteplase vs. placebo. For more details regarding the efficacy interim analysis, see Section 4.10.

For all of the aforementioned interim analyses, only the patients whose study schedules have reached the designated visits (i.e. 72-96 hours assessment for safety only interims and 90-day assessment for efficacy interim) or who have discontinued the study or died with status available to the Sponsor by the clinical cut off date will be included. Thus, patients who haven't reached the specific scheduled visits due to later study entrance will not be included.

The end of study is defined as the date when the last patient, last visit (LPLV) occurs, or the date at which the last data point required for safety follow-up is received from the last patient, whichever occurs later. This date is expected to occur 90 ± 14 days after randomization of the last patient in (LPI) the study. The total length of the study is expected to be approximately 3 years. Analysis of data from all patients will be performed when all patients have completed or discontinued the study, all data from the study are in the database, and the database is locked.

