4.6.1 Primary Efficacy Endpoint

The primary endpoint is the ordinal mRS score at Day 90. mRS is an assessment of disability with values from 0 (no symptoms at all) to 5 (severe disability); death will be scored as a 6. During the study, mRS is collected at Baseline, Day 5 or hospital discharge, and 30 and 90 days after randomization. If death occurs prior to a scheduled assessment day, the mRS will be considered available and will be set to 6. The methodology for imputations related to the primary endpoint is described in Section [4.9.1.1](#).

The distribution of mRS at Day 90 will be summarized descriptively, and plotted using Grotta bars.

Analysis of the primary endpoint will test the hypothesis as follows:

$$H_0: OR_{\{TNK \text{ vs Placebo}\}} = 1 \text{ vs. } H_1: OR_{\{TNK \text{ vs Placebo}\}} \neq 1,$$

where $OR_{\{TNK \text{ vs Placebo}\}}$ stands for the overall odds ratio of achieving a lower level vs. higher level mRS between the tenecteplase and the placebo arms. Superiority of tenecteplase over placebo will be declared if the p-value of the estimated treatment effect is ≤ 0.003 (two-sided) at the efficacy interim analysis or ≤ 0.049 (two-sided) at the final analysis, after adjustment for one efficacy interim analysis.

In case there are issues with fitting the proportional odds model (such as e.g. a quasi-complete separation), the stratified Wilcoxon-Mann-Whitney Generalized Odds Ratio statistic (WMW GenOR) as described below will be employed. Otherwise, the proportional odds assumption will be tested. For this purpose, a proportional odds model will be fitted for the Day 90 mRS outcome, which will include treatment and adjusting variables. If the p-value for the overall score test of the proportional odds hypothesis is > 0.05 , the proportional odds assumption will be deemed acceptable. The assessment of the proportional odds assumption will be independent of the results from the primary efficacy analysis from the proportional odds model.

If the proportional odds hypothesis is not rejected, the parametric proportional odds model described above will be used to analyze the primary efficacy endpoint. The estimated common odds ratio of a lower mRS score (better outcome) will be presented for treatment (TNK vs. placebo). The corresponding Wald p-value and 95% CI will also be obtained.

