4.9.1.1 Last Observation Carried Forward

For patients who died prior to completing the Day 90 study visit, the missing mRS score at Day 90 will be imputed as 6. Otherwise, missing mRS data at Day 90 will be imputed using a LOCF technique, where the missing mRS score at Day 90 will be imputed by the

last observed mRS score, Day 30 or Day 5 / hospital discharge mRS value but not the baseline value.

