One efficacy interim analysis is planned for this study, when 50% (i.e., 228) of the total patients have completed the 90-day assessment to monitor both the efficacy and safety of tenecteplase vs. placebo. At the efficacy interim analysis, a type I error rate of 0.003 will be allocated for the interim efficacy evaluation based on the Lan-DeMets theory for α -spending function that approximates the O'Brien-Fleming boundary (DeMets and Lan 1994). In case of the positive efficacy result, the iDMC may recommend to stop the trial based on the benefit-risk profile of the study drug (see Section [3.3](#)). In the event that the trial is stopped due to overwhelming efficacy results from the primary endpoint at the interim analysis, final analysis of the secondary endpoints will be performed based on the hierarchical testing procedure as described in the Section [4.6.2](#) at the 0.003 level to control the studywise type 1 error. If the study continues beyond the efficacy interim analysis, the critical value at the final primary efficacy analysis would be adjusted accordingly to maintain the protocol-specified overall type I error rate, i.e., the final efficacy analysis will be performed at the 0.049 significance level to maintain an overall family-wise type 1 error rate of 0.05.

An independent statistical entity will be responsible for conducting the interim safety and efficacy analyses and preparing the reports for iDMC review. The Sponsor will remain blinded during the course of the study.

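### Read literally, SAP 2.4 admits a patient not yet at Day 90 to the efficacy interim only if that patient has died or discontinued, and the next sentence conflicts with this

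*SAP*

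**What the plan says.** SAP 2.4 gives one inclusion rule for all interim analyses. A patient is included if the study schedule has reached the designated visit (Day 90 for the efficacy interim), "or who have discontinued the study or died with status available to the Sponsor by the clinical cut off date will be included". The next sentence reads: "Thus, patients who haven't reached the specific scheduled visits due to later study entrance will not be included".

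Other sections settle how such patients are scored. On deaths, SAP 4.6.1 says: "If death occurs prior to a scheduled assessment day, the mRS will be considered available and will be set to 6". For patients who leave alive, SAP 4.9.1.1 says: "Otherwise, missing mRS data at Day 90 will be imputed using a LOCF technique", using the Day 30 or the Day 5/discharge score.

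SAP 4.10 gives the trigger, "One efficacy interim analysis is planned for this study, when 50% (i.e., 228) of the total patients have completed the 90-day assessment", and the error spent, "a type I error rate of 0.003 will be allocated for the interim efficacy evaluation". It does not define the interim set in any other way.

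**The concern.** A patient who died or discontinued, and whose Day 90 has passed by calendar, is already covered by the schedule condition. The added clause therefore has an effect only for patients still inside their 90 days at the cut-off. Take two patients randomized on the same day, 30 days before the cut-off. The one who has died enters with mRS 6. The one who is alive and in follow-up is left out. Membership of the set depends on the outcome being tested.

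The sentence beginning with Thus does not resolve this. If it restates the rule, it removes living late entrants and keeps the selection. If it stands alone, it removes all late entrants and leaves the clause about deaths with nothing to do. Two programmers could build different sets from the same text.

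The set matters because it serves the only look that spends alpha. It gives the interim common odds ratio (or the generalized odds ratio, if proportional odds is rejected or the model cannot be fitted) and its p-value. It gates secondary testing at the interim, and it is part of the benefit-risk picture on which the iDMC may recommend stopping.

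**Working it through.** **The plan's own figures.** With the SAP Table 1 distributions, P(tenecteplase better) + 0.5 P(tie) = 0.5896. The Wilcoxon-Mann-Whitney variance is (1 - Σp̄³)/12 × 4/N, where p̄ is the mean of the two arms and Σp̄³ = 0.0216. At N = 432 and two-sided 0.049 the power is 90.2%, against the stated 90% or more. O'Brien-Fleming-type spending at half information gives 0.00305 (stated 0.003), and 0.003 with 0.049 gives 0.04998 overall. These figures reproduce.

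**Interim without late entrants.** With 114 per arm, SE = √(0.08153 × 4/228) = 0.0378 and expected z = 0.0896/0.0378 = 2.37. The critical value at two-sided 0.003 is 2.968, so the chance of crossing is Φ(2.37 - 2.97) = 27%. Expected deaths are 114 × 0.12 + 114 × 0.18 = 34.2, or 15.0% of 228.

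**Late entrants at the cut-off (assumed).** The documents give 456 patients and a total length of about 3 years. Even accrual over 36 or 24 months is 12.7 or 19 per month. Over 90 days (2.96 months) that leaves about 38 or 56 patients in the window. I assume 60-85% of their eventual 90-day deaths have been seen.

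| | 38 in window, 60% seen | 56 in window, 85% seen |
|---|---|---|
| Extra deaths, tenecteplase | 19 × 0.12 × 0.60 = 1.4 | 28 × 0.12 × 0.85 = 2.9 |
| Extra deaths, placebo | 19 × 0.18 × 0.60 = 2.1 | 28 × 0.18 × 0.85 = 4.3 |
| Total | 3.4 | 7.1 |
| Death share | 37.6/231.4 = 16.3% | 41.3/235.1 = 17.6% |
| Expected z | 2.39 | 2.42 |
| Chance of crossing 0.003 | 28% | 29% |

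Simulation of the Wilcoxon test (200,000 interims per case) agrees: 27% without the late deaths, 28-29% with them. Discontinuations add little: at 5% dropout, at most 38 × 0.05 = 1.9 to 56 × 0.05 = 2.8 patients.

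**When the shift reverses.** Suppose mortality is equal in the two arms and the benefit is purely functional. Adding a deaths to each arm of 114 multiplies the effect (the probability above minus 0.5) by w², where w = 114/(114 + a). The standard error shrinks only by about √w, so z is multiplied by about w^1.5. With a = 3.42/2 = 1.71 to 7.14/2 = 3.57, w = 0.985 to 0.970 and the factor is 0.978 to 0.955. An expected z of 2.37 falls to 2.32-2.26, and crossing falls from 27% to about 26-24%.

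**Type I error.** With no treatment effect and equal death timing, simulated two-sided error is 0.0026-0.0029 under the literal rule and 0.0028-0.0030 under an entry-date rule. Both are nominal. Now keep Day 90 outcomes equal but let death times differ by arm (mean 7 versus 40 days, assumed). Mean z moves by about 0.07 with 38 in the window, 0.10 with 56 and 0.14 with 80, toward the arm whose deaths come later. The one-sided error for benefit, nominally 0.0015, becomes about 0.0010 or 0.0019 with 56 in the window. The extremes of 0.0009 and 0.0022 need 80 in the window.

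**The case against.** The strongest reply is that the second sentence is already an entry-date rule. On that view the clause about death and discontinuation only clarifies that patients who never attend Day 90 for those reasons still count once their date has passed. The selection then disappears. This reading is available, so it cannot be said as fact that deaths will be over-represented. It makes the clause redundant, though, and the text does not choose between the readings. The need to reconcile the two sentences stands.

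The effect is also modest in the design case. Crossing 0.003 does not stop the trial by itself, because the iDMC may recommend and the sponsor decides. The calculation uses an unadjusted Wilcoxon test, while the primary analysis is a covariate-adjusted proportional odds model. All of that is fair.

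A reader might infer three stronger claims that the documents do not support:

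- **Inflated interim error.** Two-sided error is nominal with equal death timing. Unequal timing moves the one-sided error either way, by little.
- **A biased final result.** The final analysis takes place when all patients have completed or discontinued, so this selection cannot operate there.
- **A much larger distortion.** Nine extra deaths or an 18% death share would need accrual faster than about 3 years for 456 patients implies.

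**Conclusion.** The concern holds in a limited form. The literal rule makes membership of the efficacy-interim set depend on outcome for late entrants, and the following sentence contradicts it for those who have died.

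Under the stated accrual and death-timing assumptions, the design-case effect is small: about 3-7 extra deaths, a death share of about 16-17.5% instead of 15%, and 1-2 points on the chance of crossing. It grows or changes sign when mortality or its timing departs from the functional effect. That deserves attention for a thrombolytic whose monitored risk is symptomatic intracranial hemorrhage. The affected result is the interim estimate and p-value only. The plan should be changed because the correction is cheap and this is the only alpha-spending look.

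**What to change.** Give the efficacy interim its own sentence in SAP 2.4:

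- Include every patient randomized early enough that the protocol's Day 90 visit window (+14 days, Day 104) has closed by the clinical cut-off, whatever the patient's status.
- Score deaths 6 and handle a missing Day 90 mRS by SAP 4.9.1.1.
- Time the cut-off so that this set gives the planned 228, and align the trigger in SAP 4.10.
- Delete, for this analysis, the clause admitting later entrants who died or discontinued. Report their deaths in the iDMC safety tables only.

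Day 104 is preferable to a bare 90-day limit. At 90 days, living patients whose visit is still pending would have a Day 30 or Day 5 score carried forward. A small residue remains: a visit after Day 104 but inside the SAP's 61-120 day analysis window would be carried forward at the interim only.

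The cost is one sentence and one program filter, plus either a cut-off about two weeks later or a few fewer records. Over 14 days, 12.7-19 patients per month × 14/30.4 is about 6-9 patients. The iDMC loses no safety information.

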3. STUDY CONDUCT

3.1 RANDOMIZATION

Once patients' eligibility requirements are confirmed, patients are randomized 1:1 to receive a single bolus injection of tenecteplase or placebo through the Interactive Web Response System (IWRS). The study treatment kit number is also assigned by IWRS at that time. Patients are treated as soon as possible after randomization. Patients are considered enrolled in the study once they have provided the informed consent and been randomized.

Randomization is stratified by age (≤ 70 vs. >70 years of age), type of occlusion (ICA/M1 vs. M2), baseline NIHSS (≤ 15 vs. >15), and randomization site (ECC vs. nECC). A permuted block randomization is used to achieve an approximately 1:1 ratio between tenecteplase and placebo arms within each randomization stratum.

3.2 INDEPENDENT REVIEW FACILITY

An independent neurologist is contracted with the Sponsor to conduct independent imaging reading for all study related images collected by the study sites. During the study, neurological images obtained at the study sites will be sent to the independent reading center following a predefined timeline. After receiving the images, the neurologist will conduct his reading independently to collect study related neurological variables. Imaging data read by the independent neurologist will be transferred to the Sponsor on a regular basis according to a schedule agreed by both parties. Both the schedules for data transfer from study sites to independent reader and from independent reader to the Sponsor should accommodate (i.e. expedite the turnaround time) any occurrence of symptomatic intracranial hemorrhage events. More details about the role and process of independent imaging reader are provided in the independent imaging review charter.

3.3 DATA MONITORING

An independent Data Monitoring Committee (iDMC) monitors patient safety, treatment efficacy, and study conduct on an ongoing basis. Members of the iDMC are external to the Sponsor and follow a charter that outlines the iDMC roles and responsibilities. Unblinded data summaries for iDMC review will be provided by an independent statistical entity external to the Sponsor. While the iDMC will review unblinded summaries, the Sponsor will remain blinded to treatment group until the time of formal study unblinding.

During the conduct of the study, regularly scheduled safety data reviews by the iDMC will occur. After the first patient is enrolled, safety review will occur after the first 25 patients have completed the 72-96 hours assessments post-randomization and again after the first 50 patients have completed the 72-96 hours assessments post-randomization. Thereafter, the iDMC will meet at a frequency determined by the iDMC and the Sponsor according to the emerging safety profile. The iDMC or Sponsor may

also request ad hoc reviews at any time to address potential safety concerns. Additional safety reviews have been requested by the iDMC when the first 100 and 200 patients have completed the 72-96 hours assessments post-randomization.

The iDMC will also review unblinded efficacy data at the planned efficacy interim analysis when 50% of the planned patients have completed 90-day follow-up post-randomization. At this review, the iDMC will evaluate the benefit-risk profile of tenecteplase treatment through reviewing unblinded safety and efficacy data.

The iDMC may recommend stopping the study early or amending the study for either significant safety concerns or outstanding efficacy results. The final decision of acting upon the iDMC's recommendations will rest with the Sponsor. Further details about the definition, role, and the responsibilities of the iDMC are provided in the iDMC Charter.

4. STATISTICAL METHODS

Descriptive statistics will be produced for all endpoints. Categorical variables will be summarized as the number and percentage of patients or occurrences in each response category. Continuous variables will be summarized using descriptive statistics (number of observations, mean, standard deviation, median, minimum, maximum). Any required confidence intervals (CI) will be constructed as two-sided 95% CIs. Data listings will be generated for specific endpoints as appropriate.

4.1 ANALYSIS POPULATIONS

4.1.1 Efficacy Analysis Population

All efficacy analyses will be based on the intent-to-treat (ITT) population, defined as all randomized patients who provided informed consent, and analyzed according to the treatment assignment at randomization.

4.1.2 Safety Analysis Population

The Safety population is defined as all randomized patients who provided informed consent and received any amount of study drug. For safety analyses, patients will be grouped according to the treatment actually received. Patients who did not receive treatment as randomized will be listed as described in Section 4.8.1.

4.1.3 Per Protocol Population

The Per Protocol (PP) population is defined as all patients from the ITT population, who did not have any key major protocol deviations. The list of key major protocol deviations will be finalized in a blinded fashion prior to database lock.

